8.1.2 Absence seizure freedom during the 1-hour EEG at each visit (excluding dropouts)

The number and percentage of study participants who are absence seizure free based on EEG at each visit up to and including the scheduled Month 24 YEV or EDV (if prior to the Month 24 YEV) will be summarized. The Month 24 YEV may be the FV for some participants. The derivation of absence seizure freedom based on EEG is specified in [Section 3.13.3](#).

At each visit, the number and percentage of study participants who met each individual criterion will be summarized. The denominator for the percentages of absence seizure free, not absence seizure free and Criterion 1 will be based on the number of participants who are ongoing in the study at each visit; if a study participant misses a scheduled EEG and does not discontinue the

study within the protocol defined visit window for that EEG, they will be imputed as not absence seizure free at the visit. If a study participant discontinues the study early, they will not be included in the analysis for any subsequent visits. Percentages for criteria 2, 3 and 4 will be based on the number of ongoing participants in the SS who met criterion 1 at each visit.

8.1.3 Absence seizure freedom based on diary (including dropouts)

The number and percentage of study participants who are absence seizure free based on diary will be summarized at 3-month time intervals within the Evaluation Period, as defined in [Table 3-3](#), and over the entire Evaluation Period truncated at the scheduled Month 24 YEV for participants who continue in the study beyond 2 years. The latter will additionally include any diary entries collected from the end of Months 22 to 24 up to the Month 24 YEV. The derivation of absence seizure freedom based on diary is specified in [Section 3.13.4](#).

Study participants who discontinue during or prior to each 3-month period and do not meet Criterion 1 are imputed as not absence seizure free for the period of discontinuation and all subsequent 3-month periods, ending at Months 22 to 24. These participants will be separately summarized as a sub-category of not absence seizure free in the summaries.

Similarly, study participants who discontinue during the Evaluation Period and do not meet Criterion 1 are imputed as not absence seizure free for the Evaluation Period; these participants will be summarized in a sub-category as described above.

The number and percentage of study participants who met each individual criterion will also be summarized. Percentages for absence seizure free, not absence seizure free and Criterion 1 will be based on the number of participants in the SS as the denominator. Percentages for criteria 2 and 3 will be based on the number of participants in the SS who met Criterion 1 at each visit.

8.1.4 Absence seizure freedom based on diary (excluding dropouts)

The number and percentage of study participants who are absence seizure free based on diary will be summarized at 3-month time intervals within the Evaluation Period, as defined in [Table 3-3](#), and over the entire Evaluation Period truncated at the scheduled Month 24 YEV for participants who continue in the study beyond 2 years. The latter will additionally include any diary entries collected from the end of the 3-month period Months 22 to 24 up to the Month 24 YEV. The derivation of absence seizure freedom based on diary is specified in [Section 3.13.5](#). The number and percentage of study participants who met each individual criterion will be summarized, irrespective of whether the other criteria were met.

If a study participant discontinues the study during a 3-month period and does not meet Criterion 1 (as defined in [Section 3.13.4](#)) during the period of study discontinuation, the participant will be excluded from this period and all subsequent periods. If a study participant discontinues the study at any time before the Month 24 YEV, they will not be included in the analysis conducted on the Evaluation Period.

The denominator for the percentages of participants that met Criterion 1 will be based on the number of participants with data in the SS. The denominator for all other percentages for each 3-month period will be based on the number of participants who met Criterion 1 during the period. Similarly, the denominator for percentages for the analysis on the Evaluation Period (truncated at Month 24 YEV) will be the number of participants who did not discontinue the study prior to the Month 24 YEV (or FV).

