| To investigate long-term efficacy of BRV in pediatric study participants with CAE or JAE | 
• Absence seizure freedom based on diary over the entire evaluation period and by 3-month time intervals 
Estimand
 
1. Population: the study participant population as defined in the protocol-specified inclusion/exclusion criteria reflecting the target patient population.2. Study participant-level outcome: seizure freedom response on diary over the evaluation period and by 3-month time intervals.3. Intercurrent event handling: The intercurrent event of concomitant use of any permitted AED, including benzodiazepines, during each applicable 3-month period is handled in the definition of the participant-level variable implementing a composite strategy in which receiving any |

| | |
|--|---|
| | 
permitted concomitant AED, including benzodiazepines, in the 3-month period or during the visit is counted as nonresponse (ie, considered as having absence seizures).
 
The intercurrent event of diary completion during each applicable period is handled in the definition of the participant-level variable implementing a composite strategy in which completing less than 80% of diaries during the 3-month period is counted as nonresponse (ie, considered as having absence seizures).
 
4. Population-level summary measure: percentage of study participants free from clinical absence seizures.
 |
| Secondary objective | Other endpoints |
| To investigate long-term efficacy of BRV in pediatric study participants with CAE or JAE | 
 Consecutive absence seizure freedom in 6-month periods based on EEG Consecutive absence seizure freedom in 6-month periods based on diary |
| Tertiary/Exploratory | Other endpoints |

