7.3.2 Seizure diary

During the study, study participants will keep a diary to record daily seizure activity from the EV until the EDV or FV (as applicable). Study participants who discontinue study drug and require down titration will also complete their daily seizure diaries during the Down-titration Period. Study participants will be reminded to bring their diary with them to each clinic visit.

The written information is discussed with the study participants at each visit in order to ensure completeness and accuracy. As a result of the discussion, the Investigator will assess and confirm the seizures according to the ILAE codes and record the seizure types in the eCRF/diary; he/she will also confirm the presence of AEs, if applicable.

Study participants will record all types of seizures that occur in their diaries and will be educated to complete their diary entries after each seizure or at least once a day. A parent or caregiver may assist in completing the diary if necessary.

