3.2 General presentation of summaries and analyses

Statistical analysis and generation of tables, figures, study participant data listings, and statistical output will be carried out using SAS® Version 9.3 or higher. Descriptive statistics, such as the number of study participants with available measurements (n), mean, standard deviation (SD), median, minimum value, and maximum value for quantitative variables, and counts and percentages for categorical variables, will be provided. Unless otherwise noted, the denominator for percentages will be based on the set of study participants in the specified analysis set with at least 1 assessment at the time point or at least 1 assessment during the time interval being summarized.

Decimal places for descriptive statistics will always apply the following rules (with the exception of PK data):

- “ n ” will be an integer
- Mean, SD, and median will use 1 additional decimal place compared to the original data.
- Minimum and maximum will have the same number of decimal places as the original value.

The individual PK concentrations will be reported to 3 significant figures in the listing. The descriptive statistics will be rounded to 4 significant figures for the mean, geometric mean, median, SD, and confidence interval (CI), to 1 decimal place for geometric coefficient of variation and to 3 significant figures for the min, max.

Unless otherwise noted, all percentages will be displayed to 1 decimal place. No percentage will be displayed for zero counts, and no decimal will be presented when the percentage is 100%.

Unless otherwise specified (eg, for Baseline values), all outputs are based on data collected in EP0132 only, and do not include data collected in N01269. Data sources for the EP0132 EV are specified in [Section 3.3.6](#).

All outputs will be produced by actual syndrome (CAE/JAE) as reported in N01269 and for all participants. Adverse event outputs will be produced for the Evaluation Period and 3-month periods within the Evaluation Period. Selected outputs may also be produced by modal dose, maximum BRV dose, exposure duration, and 3-month periods during the Evaluation Period.

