3.13.4 Absence seizure freedom based on diary (including dropouts)

The endpoint of absence seizure freedom based on diary will be assessed at 3-month time intervals within the Evaluation Period, as defined in [Table 3-3](#), and over the entire Evaluation Period. The Evaluation Period may include any additional diary entries collected from the end of the Months 22 to 24 period up to the Month 24 YEV where the Evaluation Period is truncated for participants who reach the Month 24 YEV.

In each 3-month period (or Evaluation Period), a study participant is defined as absence seizure free if they meet all the following criteria:

1. The study participant completed their seizure diary on at least 80% of days within the relevant period. Seizure diary is defined as completed if “Diary completed” is answered “Yes” for each applicable day in the period. If “Diary completed” is answered “No” or the diary record is missing it will be defined as not completed for that day.
2. No absence seizures are reported in the seizure diaries in the relevant period
3. No concomitant use of any AEDs, including benzodiazepines during the relevant period

Specific algorithmic rules for each of the above criteria are defined as follows:

Criterion 1: Seizure diary data is reported on the Seizure Classification eCRF for at least 80% of the days within the relevant period

Criterion 2: No diary records on the Seizure Classification eCRF within the relevant period are reported with answer “Yes” to the question “Did Any Absence Seizures occur?”

Criterion 3: No records of any concomitant AED, including benzodiazepines, usage on the Concomitant Medications eCRF within the relevant period

Note that Criterion 2 and 3 will only be assessed if Criterion 1 is met. In each 3-month period (or Evaluation Period), if the study participant does not meet all the criteria for absence seizure freedom they will be regarded as not absence seizure free.

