3.13.5 Absence seizure freedom based on diary (excluding dropouts)

The endpoint of absence seizure freedom based on diary will be assessed at 3-month time intervals within the Evaluation Period, as defined in [Table 3-3](#), and over the entire Evaluation Period. The Evaluation Period may include any additional diary entries collected from the end of the 3-month Months 22 to 24 period up to the Month 24 YEV where the Evaluation Period is truncated for participants who reach the Month 24 YEV.

The derivation will be the same as [Section 3.13.4](#) apart from if a study participant discontinues or completes the study during a 3-month period then Criterion 1 will be checked and if met, the participant will be assessed for absence seizure freedom in the period of discontinuation. If they do not meet Criterion 1 during the period of study discontinuation the study participant will not be included in the analysis for that period. Additionally, they will not be included in the analysis of any period subsequent to that of study discontinuation or completion. If a study participant discontinues the study at any time before the scheduled Month 24 YEV, they will not be included in the analysis conducted on the Evaluation Period. However, if a study participant has a FV prior to the scheduled Month 24 YEV, they will be included in the analysis conducted on the Evaluation Period.

3.13.6 Absence seizure freedom based on diary with modified criterion based on seizure diary completion (including dropouts)

The endpoint of absence seizure freedom based on diary with modified criterion based on seizure diary completion (including dropouts) will be derived in the same way as the endpoint defined in [Section 3.13.4](#), however Criterion 1 will be updated to require a minimum of 50% of days of seizure diary completion within the relevant period.

3.13.7 Absence seizure freedom based on diary with modified criterion based on seizure diary completion (excluding dropouts)

The endpoint of absence seizure freedom based on diary with modified criterion based on seizure diary completion (excluding dropouts) will be assessed at 3-month time intervals within the Evaluation Period, as defined in [Table 3-3](#), and over the entire Evaluation Period. The Evaluation Period may include any additional diary entries collected from the end of the Months 22 to 24 period up to the Month 24 YEV where the Evaluation Period is truncated for participants who reach the Month 24 YEV.

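### SAP 8.1.4 and 8.1.7.2 divide the 3-month diary seizure-free percentage by diary completers only, while 3.13.5 and 3.13.7 keep ongoing non-completers in the analysis as not seizure free

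*SAP*

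**What the plan says.** The diary estimand (Protocol 1.1 and Section 3; SAP Table 2-2) treats poor diary completion as a composite outcome: "completing less than 80% of diaries during the 3-month period is counted as nonresponse". SAP 3.13.4 carries this out. Criterion 1 is diary completion on at least 80% of days, and in each period "if the study participant does not meet all the criteria for absence seizure freedom they will be regarded as not absence seizure free".

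SAP 3.13.5, the version without dropouts, takes over the 3.13.4 derivation and changes it only for participants who leave. The exclusion is for those who "do not meet Criterion 1 during the period of study discontinuation the study participant will not be included in the analysis for that period", and periods after leaving are dropped. It says nothing that removes an ongoing participant with a thin diary. SAP 3.13.7 is built the same way with 50% in place of 80%.

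SAP 8.1.4 then sets the percentages. The Criterion 1 row uses SS participants with data. For everything else, the "denominator for all other percentages for each 3-month period will be based on the number of participants who met Criterion 1" in that period. The Evaluation Period percentage in the same paragraph uses everyone who did not discontinue before the Month 24 YEV or FV. SAP 8.1.7.2 repeats all of this for the 50% threshold.

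The neighbouring sections differ. In the EEG counterpart, SAP 8.1.2, the base for the seizure-free, not-free and Criterion 1 rows is ongoing participants: "Criterion 1 will be based on the number of participants who are ongoing in the study at each visit". In SAP 8.1.3 those three rows use the whole SS, and only the later criteria are conditional: "Percentages for criteria 2 and 3 will be based on the number of participants in the SS who met Criterion 1 at each visit".

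**The concern.** The derivation puts an ongoing diary non-completer in the analysis as a nonresponder, and the denominator rule takes the same person out. With a 90-day period, Criterion 1 needs 72 completed days. A participant still in the study with 71 days completed, and absence seizures recorded on those days, is plainly not seizure free under 3.13.5, yet leaves the denominator under 8.1.4.

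This is a secondary efficacy endpoint in an open-label, single-arm study, and the discrepancy can only raise the seizure-free percentage. It also spoils two comparisons. SAP 4.1.1.1 describes each including/excluding pair as differing only in whether early discontinuers are imputed as nonresponders, but the step from 8.1.3 to 8.1.4 also changes how ongoing participants are handled. And the 50% sensitivity analysis should show what a looser completion rule does on a stable base of ongoing participants; under 8.1.7.2 the denominator moves as well.

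**Working it through.** The plan gives no figure to reproduce, since the analysis is descriptive with no power or alpha. The check is a comparison of the rules, followed by arithmetic.

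**Who is counted in a 3-month period**

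| Participant in the period | SAP 3.13.5 | SAP 8.1.4 denominator |
|---|---|---|
| Criterion 1 met | in, free or not free | in |
| Ongoing, Criterion 1 failed | in, not free | out |
| Leaves in the period, Criterion 1 failed | out | out |
| Left in an earlier period | out | out |

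The sections disagree on the second row only.

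**Formula.** Let p be the seizure-free share among participants included under 3.13.5, and d the share of those included who are ongoing and fail Criterion 1.

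- Criterion 1 met = included × (1-d).
- Nobody who fails Criterion 1 can be seizure free, so the seizure-free count is the same under both rules.
- Percentage printed under 8.1.4 = p/(1-d).
- If the not-free count follows 3.13.5, the not-free percentage = (1-p)/(1-d), and free plus not free = 1/(1-d).

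**Inputs.** Neither d nor p is in the documents, so both are assumed. Low d is possible, because at the clinic "The written information is discussed with the study participants at each visit in order to ensure completeness and accuracy" (Protocol 7.3.2).

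| d | 1/(1-d) | Printed if p = 50% | Printed if p = 20% | Free + not free |
|---|---|---|---|---|
| 5% | 1.053 | 52.6% (+2.6 points) | 21.1% (+1.1) | 105.3% |
| 10% | 1.111 | 55.6% (+5.6) | 22.2% (+2.2) | 111.1% |
| 20% | 1.250 | 62.5% (+12.5) | 25.0% (+5.0) | 125.0% |
| 30% | 1.429 | 71.4% (+21.4) | 28.6% (+8.6) | 142.9% |

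The not-free percentage alone passes 100% whenever p < d. With p = 20% and d = 30% it is 0.80/0.70 = 114.3%.

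**In counts.** Suppose all of the roughly 140 planned participants are ongoing, 126 meet Criterion 1 and 63 are seizure free. Section 8.1.4 prints 63/126 = 50.0%; the derivation gives 63/140 = 45.0%. The not-free count under 3.13.5 is 140 - 63 = 77, and 77/126 = 61.1%, so the two rows add to 111.1%.

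**Section 8.1.7.2.** The threshold is 0.5 × 90 = 45 days. Ongoing participants who fail 50% are a subset of those who fail 80%, and the included base is the same or larger because fewer leavers fail. So d, and with it the factor, is no larger than in 8.1.4. The estimand names only 80%, so this half of the conflict rests on 3.13.7 alone.

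**Bases within one table.** Seizure-free row: Criterion 1 completers. Criterion 1 row: participants with data, which on the SAP 3.2 default ("the denominator for percentages will be based on the set of study participants in the specified analysis set with at least 1 assessment") most naturally means at least one assessment in the interval, although that default yields where a section says otherwise. Evaluation Period: all who did not discontinue.

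**The case against.** The best defence is that 8.1.4 states its denominator openly, that the SAP amendment added denominator detail on purpose, and that the result is a legitimate rate among diary completers. The composite estimand is applied intact in 8.1.3 on the full SS, so the estimand result is still reported, and 8.1.4 already departs from it by dropping those who leave.

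Part of this stands. The percentage is not a miscalculation in itself, and the main conflict is with 3.13.5 rather than with the estimand. But a deliberate completers analysis does not fit the text. Section 8.1.4's own second paragraph excludes only discontinuing participants who fail Criterion 1, which would be almost redundant if every failure left the base. Its Evaluation Period denominator is not conditional on Criterion 1. Sections 8.1.1 to 8.1.3, 8.1.5, 8.1.6 and 8.1.7.1 reserve the Criterion 1 base for the later criteria. SAP 3.12, which lists changes from the protocol, mentions no removal of diary non-completers.

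Two further points stand. Sections 8.1.4 and 8.1.7.2 do not name a not-free row; it is inferred from the phrase covering all other percentages and from the layout of the sister sections, so the totals above 100% depend on that inference. The inflation of the seizure-free row does not. And with diaries checked at visits, d = 30% is an extreme case.

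**Conclusion.** The concern holds. The 3-month seizure-free percentages in the two excluding-dropouts diary tables are specified on a base that contradicts their own derivations. They come out too high by a factor 1/(1-d) whenever at least one ongoing participant fails Criterion 1 and at least one participant is seizure free. The direction is certain; the size is not, because d and p are assumed. If the not-free row is printed, it either adds with the seizure-free row to more than 100% or omits participants whom the derivation classifies.

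The reach is limited. No hypothesis is tested, 8.1.3, 8.1.7.1 and the Evaluation Period denominators are unaffected, and a reader could recover the intended figure from the counts and listings. It should be fixed, but it does not threaten the study's conclusions.

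**What to change.** In 8.1.4 and 8.1.7.2, base the 3-month seizure-free, not-free and Criterion 1 percentages on all SS participants included in that period under 3.13.5 or 3.13.7 respectively, and state that ongoing Criterion 1 failures count as not free. Keep the Criterion 1 denominator for the Criteria 2 and 3 rows, as 8.1.3 does. If a rate among diary completers is wanted, add it as a separately labelled row.

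The same edit should settle a smaller mismatch: both sections summarise each criterion regardless of the others, whereas 3.13.4 assesses Criteria 2 and 3 only once Criterion 1 is met.

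The cost is one reworded denominator paragraph in each of two sections and the matching table shells, with no new data. The seizure-free percentages fall by the factor (1-d). The Criteria 2 and 3 percentages keep their present base. The Criterion 1 percentage may shift slightly, because participants who leave in the period and fail Criterion 1 may sit in its present base.

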8.1.5 Consecutive absence seizure freedom based on EEG

The number and percentage of study participants with consecutive absence seizure freedom based on EEG by 6-month period will be summarized up to and including the scheduled Month 24 YEV. The derivation of consecutive absence seizure freedom based on EEG is specified in [Section 3.13.8](#). The number and percentage of study participants who met each individual criterion will be summarized at each visit, irrespective of whether the other criteria were met.

In addition, the number and percentage of participants with absence seizure freedom assessed cumulatively across all 6-month periods ending at Month 24 YEV will be summarized. A study participant will be categorized as absence seizure free until the 6-month period in which they are first classified as not absence seizure free. After the recurrence of absence seizures, the participant is classified as not absence seizure free regardless of whether they met the criteria for absence seizure freedom in subsequent 6-month periods.

In all summaries the percentages for absence seizure free, not absence seizure free and Criterion 1 will be based on the number of participants in the SS as the denominator. Percentages for criteria 2 and 3 will be based on the number of participants in the SS who met Criterion 1 at each visit.

